## 2. Background

Urinary incontinence, or accidental loss of urine, is a common problem that affects 10-30% of all women with the majority of incontinence attributed to stress urinary incontinence (SUI) or mixed urinary incontinence (MUI) (1). Prior studies have shown that pelvic floor physical therapy (PFPT) and biofeedback training are both excellent non-surgical options and are recommended as first-line therapy (2) for SUI (leaking with laugh, cough, and sneeze). Both the American Urologic Association and the International Urogynecologic Association recommend PFPT as first-line therapy for SUI (2). Many areas of the country do not have qualified PFPT and

**PROTOCOL TITLE: SQEASI: Systematized Quality Exercise Alternatives for Stress Incontinence**

the community outpatient rehabilitation referral is often limited for patients in rural areas that must travel to larger city centers for PFPT. Women who live far from PFPT facilities also must travel great distances to see medical providers for their incontinence and attend multiple PFPT appointments. Though physical therapists have used biofeedback for 20 years, several FDA approved devices for home biofeedback have been introduced to help treat women with SUI at home. Regarding these devices, there is limited information available comparing them to the standard of care. If home biofeedback is equivalent to standard of care PFPT for SUI, patients can obtain treatment in the privacy of their homes with a home devices that may offer similar quality of life improvements for SUI without the inconvenience of travel, cost and personal distress as PFPT. To solve the problem of limited PFPT services and the obstacles obtaining PFPT, we propose to study at home biofeedback devices versus PFPT for women with SUI. This innovative research shows promise in helping our patients overcome an embarrassing and costly condition in the privacy of their own homes on their own time.

### **3. Study Design**

We plan to perform an unmasked, non-inferiority randomized controlled trial to determine if quality of life is improved with use of PFPT or home biofeedback linked to smartphone for stress urinary incontinence. The target population are those patients with stress urinary incontinence who present to the urogynecology clinic either at University of New Mexico Hospital (UNMH) or Sandoval Regional Medical Center (SRMC). Women will be informed which arm of the study they are randomized to as this is required for treatment. Masking is not possible with this study design, as participants either do or do not receive a biofeedback device. All women will give written consent prior to enrollment.

### **4. Inclusion and Exclusion Criteria**

We will recruit patients who present to the University of New Mexico Urogynecology and Gynecology practices at UNM Eubank Clinic (UNM) or Sandoval Regional Medical Center (SRMC) with pure stress urinary incontinence or mixed urinary incontinence with stress predominant symptoms who have never had an anti-incontinence procedure in the past or formalized PFPT. They also cannot be currently using a pessary. To confirm diagnosis and eligibility, we will conduct a history and physical, complete with cough stress test and POP-Q pelvic examination. A cough stress test requires the patient to cough or Valsalva in lithotomy or standing position to assess for leakage of urine and is part of our routine standard of care when evaluating urogynecologic issues. Urinary leakage during this test indicates SUI. If the patient notes >50% of incontinence symptoms from SUI, she will be introduced to the study and provided with written information that may help her decide if participation in the study is right for her. All patients will be counseled about possible treatment options for stress urinary incontinence including non-surgical and surgical techniques. If a woman declines to participate

PROTOCOL TITLE: *SQEASI: Systematized Quality Exercise Alternatives for Stress Incontinence*

or is withdrawn from the study either by her desire or that of the research staff, she will be offered the same treatment options. Her follow up appointments will be the same regardless of participation in the study.

The rationale for targeting this population is that these are women who would routinely undergo conservative management for their condition initially. Patients will be enrolled if they meet the inclusion and do not meet the exclusion criteria.

The inclusion criteria are:

- Female Subjects >18 years of age
- SUI or Mixed UI with stress predominant symptoms and more bother by the SUI
- English speaking/reading
- Own a smartphone that can support phone application and Bluetooth for the biofeedback device and be able to upload a smartphone application with minimal instruction
- Willing to come for 4 PFPT visits over 3 months if randomized

Exclusion criteria:

- Prior anti-incontinence surgery
- Had prior pelvic floor physical therapy for SUI
- Prolapse of any compartment noted below the hymen
- Inability to speak/understand English
- Pregnant
- Decline or unable to return for frequent PT visits during study period
- Unable to be contacted for follow up by telephone
- Neurologic disorders known to cause neurogenic bladder
- Plan to continue using a pessary after potential enrollment visit

We have decided to only include adults who are capable of giving informed consent. Children, prisoners and pregnant women will not be included. Additionally, the phone app is only available in English, therefore non-English speaking patients are excluded.

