**PROTOCOL TITLE: SQEASI: Systematized Quality Exercise Alternatives for Stress Incontinence**

will be recruited in the UNM Eubank and SRMC clinic. All patients will have a complete history and physical taken. They will undergo a pelvic exam where they will be instructed on how to perform a pelvic floor contraction correctly and a cough stress test will be performed as part of the standard of care. After recruitment, they will undergo the consent process, and fill out initial questionnaires in the outpatient offices. Patients randomized to the biofeedback group will be given their devices in clinic and research staff will assist in setting up the device and downloading the phone app. The patients randomized to physical therapy will have their PFPT at the UNM Eubank clinic. To standardize therapy for these women all of our pelvic floor physical therapists will provide women with the same set of exercises and standard schedule of one initial visit and 3 follow up appointments. All other follow-up will be performed in the above-mentioned outpatient clinics.

There are no laboratory tests in this trial other than what would routinely be collected for the workup of SUI, nor is there involvement of any community advisory board. We do not perform urodynamic studies prior to managing patients with SUI with conservative therapy, so this study will not be performed. Also, there will not be any research conducted outside of the UNM HSC and its affiliates.

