## **12. Study Procedures**

This non-blinded, non-inferiority randomized controlled trial will be conducted at the UNM Eubank Clinic and SRMC Urogynecology clinic. Each site will recruit participants and we will plan to obtain up to 75 between the two sites. Collaborating investigators will be members of the Urogynecology Division at UNM HSC.

The primary aim of our study is to determine if quality of life is improved with use PFPT versus home biofeedback therapy alone in women with SUI. The target population will be patients with SUI who are seeking care. The current recommendation is to advise patient undergo conservative management with PFPT, try an incontinence pessary, or request the patient perform exercises at home. For all patients who present for treatment of SUI, we will take a thorough history and physical (including a POP-Q pelvic examination), score vaginal muscle strength based on Modified Oxford Grading Scale, perform a cough stress test to assess for SUI, and counsel the patient on all of her options including medical and surgical interventions.

If the patient is interested in conservative management and fulfills study inclusion criteria, we will then offer her the choice of volunteering for the study. All women will give written consent prior to their enrollment at this time and fill out questionnaires in the clinic. Research staff and clinicians will obtain consent and administer study questionnaires. After enrollment, participants will fill out baseline surveys, including the International Consultation on Incontinence Questionnaire- Short form (ICIQ-SF), Incontinence Severity Index (ISI), European Quality of Life-5 dimensions (EQ-5D), Overactive Bladder Questionnaire short form (OAB-q SF) Pelvic Organ Prolapse Incontinence Sexual Questionnaire (PISQ-12), and Female Sexual Function Index (FSFI). Data collected in addition to the above outcome measures includes patient demographics, medical/surgical History, and contact information, which are attached as supporting documents. This information will be collected from the patient on the day of enrollment and we will review the patient's medical record if information is missing or unclear.

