Randomization assignment will be generated by computer based randomization table and assigned by a research coordinator not otherwise involved in the study. Assignments will be kept in sealed opaque envelopes numbered sequentially. On the day of the patient's clinic visit, after signing consent and deciding to participate, the research coordinator will bring the next envelope in the sequence will be opened, randomizing the patient to PFPT or home biofeedback. The therapy allocation will then be carried out.

The biofeedback group will be given a PeriCoach® biofeedback device, which has a Bluetooth connection to a smartphone, free of charge. The smartphone application will be uploaded during the visit and linked to the device to ensure the patient understands how to

PROTOCOL TITLE: *SQEASI: Systematized Quality Exercise Alternatives for Stress Incontinence*

install the program. An information sheet with recommendation for exercise frequency will be given at the time of enrollment to provide recommendations for use. All participants will start as a beginner in the program and works up to a maintenance level. At the end we expect they will be doing 15 exercises, 3 times per day per manufacturer's instructions. 2 weeks following enrollment, these patients will be called to ensure they understand how device functions and are not having technical difficulties. When the patient returns for the 3 month follow up the smartphone app will be reviewed as the app records how often the patient performs the exercises. If that is not available, we will have the patient self-report her exercise frequency.

For patients randomized to physical therapy, PFPT will be scheduled for 4 sessions over 3 months, as is common practice for patients with SUI. These patients will receive instructions on how to engage their core, contract their vaginal muscles, as well as recommendations for home exercises to be performed for 3 sessions per day. The first session will be to establish the patient's baseline abilities with follow up sessions to reinforce instructions, performance of exercises and to ensure the patient is improving. Patient compliance of attending PT sessions will be recorded, as will the amount each patient spends in co-pays per session. After 3 months, regardless of the number of appointments the patient has attended, she will return for a follow up visit to assess how well she is doing.

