## **15. Withdrawal of Subjects**

Any participant may withdraw from the study at any time without penalty and will continue to receive the clinical standard of care. A subject may be withdrawn from the study without her consent at the discretion of the physician and study staff if they believe she no longer meets study inclusion criteria or if she meets exclusion criteria, or if they believe that it is not in her best interest to continue study participation. Investigators may withdraw a subject if the subject is not following the study protocol. If a woman is withdrawn from the study either at her own discretion or that of the research staff, she may continue with conservative or surgical management of her SUI in the usual fashion.

To minimize withdrawal from the study, patients will be randomized just after deciding on non-surgical management and signing consent. According to the 2010 CONSORT guidelines, we will analyze all participants assessed for eligibility within the study. We will document reasons for withdrawal from the study including failure to meet eligibility criteria or participant declining enrollment into the study. We will report eligibility criteria not met or reasons for declining participation in the study. The withdrawal procedure is clearly documented in the study consent.

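### App ability is an entry criterion for both arms but is seen to be exercised only after allocation and only in the biofeedback arm, and the withdrawal rule then allows removal on it, with no as-randomized analysis set to prevent this

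*Combined protocol and SAP*

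**What the plan says.** **The criterion.** Section 4 makes it a condition of entry, whatever the arm, that a woman own a compatible Bluetooth phone and "be able to upload a smartphone application with minimal instruction". The steps that Section 4 names for confirming eligibility are clinical: history, physical examination, cough stress test and POP-Q. Section 12 adds pelvic floor strength grading and counselling. Neither mentions the phone.

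**The order of events.** Eligibility is meant to come first: "Patients will be enrolled if they meet the inclusion and do not meet the exclusion criteria". The envelope is opened at the same visit: "On the day of the patient's clinic visit, after signing consent and deciding to participate". Section 12 then says, for the biofeedback group, "The smartphone application will be uploaded during the visit and linked to the device". Section 8 says, again for that group, that "research staff will assist in setting up the device and downloading the phone app". No phone or app step is described for PFPT.

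**Removal.** Section 15 allows withdrawal without the woman's consent. Clinicians and staff may use this power "if they believe she no longer meets study inclusion criteria or if she meets exclusion criteria". Section 3 states that the trial is unmasked.

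**Analysis.** Section 13 names the tests but no analysis set and no rule for missing outcomes. Section 15 speaks of analysing everyone assessed for eligibility. That group includes women who were never randomized, so it cannot define the set for a 3-month between-arm comparison.

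**The concern.** Ability to install an app is something a woman shows by doing it. As the procedures are written, staff first watch this happen after they know the allocation, and only in one arm. If the phone will not run the app or the woman cannot manage it, a written rule lets them conclude that she was not eligible after all. A woman with the same phone and the same difficulty in the PFPT arm would never come to notice.

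Women who cannot operate the device might well be those in whom home biofeedback does least. If they leave the biofeedback arm, its mean ICIQ-SF improvement would look better than it would among all women allocated to it. In a non-inferiority trial, an error in that direction supports the claim being tested. With about 25 women per arm, two or three removals matter.

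**Working it through.** **1. The plan's own figure.** Sections 5 and 13 give a 4-point margin, alpha 0.05, 80% power and 21 women per group. They give no SD and do not say whether alpha is one-sided or two-sided, so the 21 cannot be confirmed directly. Solving backwards with the noncentral t distribution, 21 per group corresponds to an SD of 5.12 at one-sided 0.05, or 4.51 at one-sided 0.025. Normal-approximation check of the first: n = 2 × 5.12² × (1.645 + 0.842)² / 4² = 20.3, which rounds up to 21. Both SDs are assumptions.

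**2. Standard error.** 5.12 × √(2/21) = 1.58 points.

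**3. Shift caused by removal.** If a fraction p of biofeedback women is removed, and their change would have been g points worse than that of the remaining biofeedback women, the arm mean moves by p × g. Section 5 gives 25 per group, so 1, 2 or 3 removals are p = 0.04, 0.08 or 0.12. With g = 5 the shifts are 0.2, 0.4 and 0.6 points, which is 5%, 10% and 15% of the margin. The counts and the gap are assumptions; the documents give neither.

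**4. False non-inferiority rate.** Let biofeedback truly be 4 points worse among all randomized women, so that a non-inferiority claim is wrong. The rate is approximately Φ(p × g / 1.58 − 1.645). For one removal at g = 5 this is Φ(0.127 − 1.645) = Φ(−1.518) = 6.5%; the noncentral t gives 6.4%. The table uses the noncentral t, holds the standard error at 1.58 and starts from 5%.

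| Gap g (points worse) | 1 of 25 removed | 2 of 25 | 3 of 25 |
|---|---|---|---|
| 7 | 7.1% | 9.7% | 13.1% |
| 5 | 6.4% | 8.1% | 10.2% |
| 3 | 5.8% | 6.7% | 7.8% |
| 0 | 5% | 5% | 5% |
| −4 (removed women would have done better) | 4.1% | 3.3% | 2.6% |

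**5. Other settings.** At one-sided 0.025 with SD 4.51 and a 5-point gap, the rate goes from 2.5% to 3.4%, 4.7% and 6.2%. A separate normal-approximation calculation allowed for 20% dropout and for the smaller biofeedback arm, with SD 5.2 and a 4-point gap. It took the rate from 5% to 6.1%, 7.3% and 8.7%.

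**The case against.** The strongest reply is that the plan does put eligibility first. Besides the enrolment rule in Section 4, Section 12 says "If the patient is interested in conservative management and fulfills study inclusion criteria, we will then offer her the choice of volunteering for the study". Staff may simply ask about the phone, or look at it, before consent. A reader might infer that the criterion is tested only after allocation. The documents do not say so; they only leave any earlier check undescribed.

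Set-up is also presented as training, not as a test of eligibility: "The smartphone application will be uploaded during the visit and linked to the device to ensure the patient understands how to" install the program. Staff help with it and telephone two weeks later about technical problems. If app records are missing at 3 months, exercise frequency is taken by self-report, and all participants are due a 3-month visit with a telephone fallback. Nothing links a failed set-up to removal. This makes removal less likely, but it does not withdraw the discretion given in Section 15.

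A reader might also infer that removal can occur in the biofeedback arm alone. That holds for the app criterion only. The criteria on willingness and ability to attend PFPT visits are put to the test only in the PFPT arm, and Section 15 reaches them too. Removing poor attenders could flatter PFPT and partly offset the bias. Section 12 does bring PFPT women back however many sessions they attended, and has no matching sentence for failed device set-up, so an offset cannot be relied on.

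Finally, the direction is not fixed. Withdrawn women are offered the usual treatment options. One who moved to PFPT might do better than the biofeedback women who stayed, and removing her would work against non-inferiority.

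All of this limits the point without removing it. The plan still permits unmasked removal on a criterion exercised in one arm, and nothing in the analysis section prevents it.

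**Conclusion.** The point holds as a conditional risk. A described one-arm set-up step, a discretionary withdrawal rule and the lack of an as-randomized analysis set together allow selective removal from the biofeedback arm. For the smartphone criterion the likelier direction favours non-inferiority, provided that set-up failures are removed and would have done worse. For 1 to 3 removals from 25 at a 5-point gap, the false non-inferiority rate would rise from 5% to about 6% to 10%; gaps of 3 to 7 points widen this to about 6% to 13%. The SD, one-sided alpha, removal counts and gaps are all assumed.

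The documents do not support reading this as an established bias towards non-inferiority, nor as one that only an earlier check could cure. Following all randomized women and analysing them as allocated would stop this selective removal wherever the check is placed.

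**What to change.** 1. **Section 12, before the envelope is opened.** For every woman, after consent, confirm on her own phone that Bluetooth works and that the free app can be installed with the minimal instruction allowed. Record the result. Treat a failure as a screen failure and do not randomize.
2. **Sections 15 and 13.** State that set-up, pairing or attendance problems found after randomization are not grounds for removal from follow-up or analysis. State that the 3-month ICIQ-SF of every randomized woman is sought and analysed in her allocated arm, with a per-protocol analysis alongside.

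The second part is the essential protection, because pairing with the device itself would still be tried only in the biofeedback arm. The first part reduces how often the problem arises.

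The cost is a few minutes per woman at a visit already taking place, a few more screen failures, and slight exposure of PFPT women to the app. The sample size calculation is unaffected.

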## 5. Number of Subjects

The primary outcome of this study is improvement in incontinence quality of life as measured by the ICIQ-SF Questionnaire. We used the previously reported means and standard deviation for this questionnaire (3) from a prior RCT on biofeedback and pelvic floor exercises. We have powered the study based on a 4-point difference as significant between groups. This 4-point difference used for the power calculation is based on prior studies and the minimally important difference that has been previously established (4). To achieve power for this non-inferiority RCT demonstrating a difference between groups of less than 4 points we need 21 patients per group (biofeedback versus PFPT) to detect no difference with an alpha =0.05 and

## PROTOCOL TITLE: *SQEASI: Systematized Quality Exercise Alternatives for Stress Incontinence*

with 80% power. Allowing for a dropout of 20% we will enroll at least 50 patients (or 25/group), but up to 75 total.

This is a not a multi-center study. Data will be housed at the Eubank clinic

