### 6. Study Timelines

Based on current clinic volume in the UNM division of Urogynecology, we estimate recruitment of up to 75 patients would be feasible over a 12 month period. A review of our clinic calendar revealed in 1 months' time, the urogynecology division typically sees 10-20 patients who would meet criteria for our study. Assuming 50% enrollment, we will be able to recruit our projected number of patients in 12 months. Additionally, as subjects will be followed for 3 months after randomization, we expect it may take up to 15 months to collect 3 month follow up data. We estimate that data analysis and composition of the manuscript will take an additional 10 months.

Timeline	July 2018- Oct 2019	Nov 2019-Feb 2020	Mar 2017-May 2020
Subject recruitment, therapy, through 3 month follow up	←→		
Data analysis		←→	
Manuscript preparation		←→	

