Three months after starting active treatment, all participants will have a return visit to discuss progress, which is consistent with our standard care for these patients. If the participant had a delay in starting PFPT, the follow up visit will occur 3 months after first PT appointment. At the 3 month visit the patient will complete the ISI, ICIQ-SF, EQ-5D, OAB-q SF, PISQ-12, FSFI, and PGI-I. We will also ask the patient which treatment she would prefer if given the option, the level of satisfaction she has with the current treatment, and if she is planning any future surgical procedures or treatment for her stress incontinence. A physical exam will assess pelvic floor strength using the Modified Oxford Grading Scale and a cough stress test will be performed. If the patient is unable to return to clinic, a member of the research team will call the patient to administer the surveys over the phone. If unable to contact the patient 3 times, we will discontinue attempts and the patient will be considered lost to follow up.

Table 1: Outcomes collected at various time points

	Baseline	3 months
Demographic and medical history	X	
ISI	X	X
Revised Oxford Scale	X	X
ICIQ-SF	X	X
EQ-5D	X	X

FSFI	X	X
OAB-q SF	X	X
PISQ-12	X	X
PGI-I		X
Follow up Questionnaire		X

Our primary outcome is changes in QOL at 3 months after treatment initiation as measured by the ICIQ-SF. It is our standard of care to see patients back at 3 months following SUI treatment initiation to assess for continued leakage and offer further conservative or surgical management. Therefore, as part of a secondary aim we will assess sexual function, compliance with treatment between groups, preference between 2 options, and desire for further treatment at this 3 month time point.

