## **13. Data Analysis**

Data Analysis: Between and within group differences will be evaluated using Fisher's exact test for categorical variables and t-tests for continuous variables. If there are any baseline differences between groups, a multivariate analysis will determine the contribution of these differences to observed differences (if any) between groups.

Power Analysis: Power analysis was performed based on previously reported means and standard deviation for the ICIQ-SF questionnaire. The primary outcome of this study is improvement in incontinence quality of life as measured by the ICIQ-SF Questionnaire. We used the previously reported means and standard deviation for this questionnaire (10) from a prior RCT on biofeedback and pelvic floor exercises. We have assumed a change score of greater than 4 points to be significant between groups based on prior studies and the minimally important difference that has been previously established (11). To achieve significance for a non-inferiority study using these assumptions we would need 42 patients, 21 per group to detect this difference with alpha =0.05 and with 80% power. To allow for a dropout of 20% we will enroll at least 50 patients, but up to 75 to account for participants who are lost to follow up.

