**23. Compensation**

For completion of the study, each patient will be compensated with a merchant gift card worth \$50 total. They will receive a \$10 gift card at their initial study visit (enrollment) and \$40 gift card at their 3-month follow-up visit in the form of Target gift cards. This payment is reasonable compensation for the inconvenience of participating in a research study due to the additional time the study questionnaires will require from the participant.

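### The minimum enrolment of 50 absorbs 16% dropout, not the stated 20%: at 20% it leaves 40 evaluable women against the 42 required

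*Combined protocol and SAP*

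**What the plan says.** The sample-size target appears in two places in the combined protocol and SAP.

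- Section 5 (Number of Subjects) asks for 21 women per group and continues: "Allowing for a dropout of 20% we will enroll at least 50 patients (or 25/group), but up to 75 total".
- Section 13 (Data Analysis, power paragraph) gives the same target, "we would need 42 patients, 21 per group to detect this difference with alpha =0.05 and with 80% power", and the same allowance, "To allow for a dropout of 20% we will enroll at least 50 patients". It then adds "but up to 75 to account for participants who are lost to follow up".

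The checklist item III (Medical Devices) plans devices for 25 women in the biofeedback arm, which matches a total of 50. No section says when enrolment must continue past 50.

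**The concern.** Both sections tie the 20% allowance to the minimum of 50. A trial that enrolled exactly 50 would comply with the protocol. If it then lost the 20% it had planned for, it would still miss its own evaluable target. In a non-inferiority trial, fewer evaluable women mean a wider confidence interval and a harder task in excluding the margin. The sample-size statement is the plan's own standard of adequacy, so its two figures, the dropout rate and the minimum, should agree.

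**Working it through.** **Inputs.** Required evaluable: 21 per group, 42 in total (Sections 5 and 13). Planned dropout: 20% (both). Minimum enrolment: 50, or 25 per group (Section 5). Ceiling: 75 (both).

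**Where 50 appears to come from.** Multiplying by (1 + dropout) gives 42 × 1.2 = 50.4 and 21 × 1.2 = 25.2. Rounded down, these are the plan's 50 and 25.

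**What 20% dropout requires.** Enrolment = evaluable / (1 − dropout).

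- In total: 42 / 0.80 = 52.5, so 53.
- Per group: 21 / 0.80 = 26.25, so 27, which is 54 with equal arms.

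**What 50 delivers at 20% dropout.** 50 × 0.80 = 40 in total and 25 × 0.80 = 20 per group. That is two short in total and one short per group.

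**Dropout each total can absorb before falling below 42**, from 1 − 42/N:

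| Enrolled | 50 | 51 | 52 | 53 | 54 | 75 |
|---|---|---|---|---|---|---|
| Dropout absorbed | 16.0% | 17.6% | 19.2% | 20.8% | 22.2% | 44.0% |

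**Effect on power.** The documents give neither the SD nor the sidedness of alpha, so this step rests on assumptions: a one-sided non-inferiority t-test, margin 4 points, true difference 0, and 21 as the smallest group size reaching 80%. Power is 1 − F(t(1−α, 2n−2)), where F is the noncentral t distribution with 2n−2 degrees of freedom and noncentrality 4 / (SD × √(2/n)).

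| One-sided alpha | SD range consistent with n = 21 | Power at 21 per group | Power at 20 per group |
|---|---|---|---|
| 0.05 | 4.996 to 5.124 | 80.0% to 81.7% | 78.2% to just under 80% |
| 0.025 | 4.400 to 4.514 | 80.0% to 82.0% | 78.0% to just under 80% |

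**Chance of reaching the target.** If each woman drops out independently with probability 20%, the number evaluable is Binomial(N, 0.8).

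| Enrolled | At least 42 in total | At least 21 in both arms |
|---|---|---|
| 50 (25 per group) | 31% | 0.421² = 18% |
| 54 (27 per group) | 73% | 0.713² = 51% |

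At 54 the expected count is 54 × 0.80 = 43.2 (21.6 per group). So 54 meets the target in expectation but does not guarantee it.

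**The case against.** The strongest reply is that 50 is only a floor. Section 13 links the ceiling of 75 to loss to follow-up, and Section 6 plans recruitment of up to 75. Section 6 says the clinic "typically sees 10-20 patients who would meet criteria for our study" each month. With half enrolling, even the slowest rate is 5 a month, so 12 months gives 60 women and 60 × 0.80 = 48 evaluable, above 42. Retention is also protected in several ways:

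- Section 4 excludes women who cannot be followed up by telephone.
- Under Section 12, women in the physical therapy arm return at 3 months however many sessions they attended.
- For women who cannot attend, Section 12 says "a member of the research team will call the patient to administer the surveys over the phone".
- Section 23 pays $40 of the $50 at the 3-month visit.

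All of this stands, and it makes a shortfall less likely. It does not make the sentence correct: the ceiling permits enrolment beyond 50 without requiring it, and the device count of 25 describes the trial at its minimum.

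A second objection concerns power. The limit of about 2 points depends on the non-inferiority reading. Section 5 also speaks of detecting no difference. If the test were two one-sided equivalence tests, power at 20 per group would be about 77%, a loss of about 3 points. That is fair, and it is a reason to keep power figures out of the corrected text. The arithmetic error does not depend on it.

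**Conclusion.** The concern holds. The minimum of 50 allows for 16% dropout, and the statement that it allows for 20% is wrong in Sections 5 and 13. This follows from the plan's own figures and needs no outside source, SD or choice of alpha.

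The practical effect is small. It arises only if enrolment stops at 50 to 52 (or, counted per group, with fewer than 27 in an arm) and dropout reaches about 20%. At 50 the shortfall is two evaluable women, and the loss against 80% power is above 0 and at most about 2 percentage points under the non-inferiority assumptions in the working. The correction should be made because the wrong figure stands in both sample-size statements and is easily repaired. It does not call the trial's validity into question.

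**What to change.** Either of two changes, made in both Section 5 and Section 13, resolves the point.

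1. **Restate the allowance.** Say that 50 enrolled allows for 16% dropout, and that at 20% dropout 40 women would be evaluable against the 42 required. Give no power figure unless the SD and the sidedness of alpha are also stated. This costs wording only. It corrects the statement but leaves the minimum where it is.

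2. **Raise the minimum to 54 (27 per group)**, within the existing ceiling of 75. This means four more women, two more devices at the investigators' cost, and 4 × $50 = $200 in gift cards (Section 23). At the 5 to 10 enrolments a month implied by Section 6, four women add 4/10 to 4/5, or 0.4 to 0.8 months. Reaching 54 takes 54/10 to 54/5, or 5.4 to 10.8 months, inside the planned 12.

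The second option also requires changing the 25 biofeedback patients in checklist item III to 27. That count already falls short for any equal-arm enrolment above 50 (37 or 38 women at the ceiling of 75), so it is worth aligning if enrolment beyond 50 is intended.
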